7.1.2. Data Handling Rules

Missing data will not be imputed. If the severity or relationship of AEs to the study vaccine could not be derived (ie, missing or unknown), it will be considered as unknown, for analysis purposes. Local solicited AEs will be considered as related with the use of the study vaccine, by definition.

Solicited events will always be allocated to the analysis period (Section 2.1). For analysis purpose, the AEs will be allocated to periods and/or phases as described in Attachment 1.

7.1.3. Analysis Methods

In general, the AEs following vaccination will be summarized (ie, tables of descriptive statistics) by vaccination schedule and presented per period/phase. Similar summary tables will also be provided pooled by vaccine (dose).

Furthermore, unsolicited AEs will be summarized (showing number and percentage) by System Organ Class (SOC) and Preferred Term (PT). Solicited AEs (recorded by day) will be converted into the analysis format of unsolicited AEs (recorded by event) as detailed in Attachment 2. These solicited AEs will be summarized by class (local, systemic) and Preferred Term. For solicited as well as unsolicited AEs, tables focusing on severity will be created. Focus will also be on the relationship (to the study vaccine) of the solicited systemic and unsolicited AEs.

The SAEs, AEs with fatal outcome, AEs leading to permanent discontinuation from study vaccination, Grade 3 AEs and IREs will also be listed. A table summarizing all those parameters will further be created and presented per analysis period and vaccination schedule. Summary tabulations by SOC and PT for each of the category of events (ie, SAEs, AEs with fatal outcome, AEs leading to permanent discontinuation from boost vaccination, Grade 3 AEs and immediate reportable events) will also be generated on the entire reporting period. Subject narratives will be generated for these events, except Grade 3 AEs. For Grade 3 AEs, the narratives will only be generated for those AEs that are considered related to study vaccination.

For the solicited local and systemic AEs, the duration and time to first onset of the events will also be summarized. If a subject experiences more than 1 occurrence of a solicited event, the maximum duration of the events will be used. The time to first onset is defined as:

$$[\text{date of first onset} - \text{reference date} + 1]$$

The reference date is the start date of each vaccination period (ie, Post-dose 1, Post-dose 2 or Post-dose 3). Duration and time to onset of AEs will be expressed in days.

7.2. Clinical Laboratory Tests

This section concerns the clinical laboratory test data. The analysis of the laboratory assessments will be based on the Food and Drug Administration (FDA)'s Toxicity Grading Scale for Healthy Adult and Adolescent Volunteers Enrolled in Preventive Vaccine Clinical Trials (Attachment 3 and Attachment 5) and the DMID Pediatric Toxicity Tables for Children Greater Than 3 Months of Age (Attachment 4) as appropriate. In case no toxicity grades are defined for a test, the abnormalities above or below the normal range will be used.

It is important to note that any abnormal laboratory value that represents a clinically relevant increase in toxicity grade post study vaccination is also recorded on the AE page of the eCRF and will be analyzed as AEs.

7.2.1. Definitions

In determining toxicity grades, the following rules will be applied:

- Worst grades/abnormalities are determined over the entire period (eg, Post-dose 1, Post-dose 2 or Post-dose 3) separately, including all post-baseline measurements of the corresponding period.
- The abnormalities “abnormally low” and “abnormally high” are considered equally important and both abnormalities are shown in the tables. (This means that the sum of the percentages can exceed 100%).
- If a laboratory value falls within the grading as specified in the grading table but also within the local laboratory normal limits, the value is considered as normal or Grade 0.
- Laboratory results falling between the grading scales will be allocated to the adjacent worst-case grade (because the scale for some parameters in the grading table is not continuous as there may be zones where toxicity grade definitions do not exist).

An abnormality (toxicity grade or abnormality based on normal ranges) will be considered as following vaccination in a period and/or phase if it is worse than the corresponding baseline record. If the baseline value is missing, the abnormality is always considered as following vaccination. A shift from “abnormally low” at baseline to “abnormally high” post-baseline (or vice versa) is also considered as an abnormality following vaccination.

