At least one general symptom was reported in two fifths of the subjects following MVA-BN-Filo administration. The most common general symptoms were fatigue, headache, myalgia (muscle pain) and nausea. All general symptoms were transient and resolved without lasting effects.

Changes in laboratory tests were reported following MVA-BN-Filo administration which included hypokalemia and decreased numbers of neutrophils (neutropenia). Both changes in laboratory tests were seen in similar numbers of participants following MVA-BN-Filo and the dummy (placebo) vaccine. Less frequently, events of decreased hemoglobin levels were reported. The changes in laboratory tests were not associated with any complaints or symptoms.

Extensive nonclinical studies support the safety profile of the MVA-BN strain.

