Fatigue/malaise	Minimal symptoms; caused minimal or no interference with work, school or self-care activities	Notable symptoms; required modification in activity or use of medications; did not result in loss of work or cancellation of social activities	Incapacitating symptoms; required bed rest and/or resulted in loss of work or cancellation of social activities	
Myalgia	Minimal symptoms; caused minimal or no interference with work, school or self-care activities	Notable symptoms; required modification in activity or use of medications; did not result in loss of work or cancellation of social activities	Incapacitating symptoms; required bed rest and/or resulted in loss of work or cancellation of social activities	
Arthralgia	Minimal symptoms; caused minimal or no interference with work, school or self-care activities	Notable symptoms; required modification in activity or use of medications; did not result in loss of work or cancellation of social activities	Incapacitating symptoms; required bed rest and/or resulted in loss of work or cancellation of social activities	
Chills	Minimal symptoms; caused minimal or no interference with work, school or self-care activities	Notable symptoms; required modification in activity or use of medications; did not result in loss of work or cancellation of social activities	Incapacitating symptoms; required bed rest and/or resulted in loss of work or cancellation of social activities	

LABORATORY TOXICITY GRADING

Grading scale used for lab assessments is based on 'FDA's Toxicity Grading Scale for Healthy Adult and Adolescent Volunteers Enrolled in Preventive Vaccine Clinical Trials', but grade 3 and 4 are pooled below, consistent with the 3 scale toxicity grading used throughout the protocol. If a laboratory value falls within the grading as specified below but also within the local laboratory normal limits, the value is considered as normal. For hemoglobin only the change from reference is used for the grading. The FDA table does not include toxicity grading for hematocrit, RBC counts or INR.

Blood, Serum, or Plasma Chemistries ^a	LO/HI/N ^b	Mild (Grade 1)	Moderate (Grade 2)	Severe (Grade 3)
Sodium (mEq/L or mmol/L)	LO	132-134	130-131	≤129

^a Depending upon the laboratory used, reference ranges, eligibility ranges and grading may be split out by sex and/or age.

^b Low, High, Not Graded.

	HI	144-145	146-147	≥ 148
Potassium (mEq/L or mmol/L)	LO	3.5-3.6	3.3-3.4	≤ 3.2
	HI	5.1-5.2	5.3-5.4	≥ 5.5

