Glucose (mg/dL)	LO	65-69	55-64	≤ 54
	HI ^a	100-110	111-125	>125
	HI ^b	110-125	126-200	>200
Blood urea nitrogen (mg/dL)	HI	23-26	27-31	>31
Creatinine (mg/dL)	HI	1.5-1.7	1.8-2.0	>2.0
Calcium (mg/dL)	LO	8.0-8.4	7.5-7.9	<7.5
	HI	10.5-11.0	11.1-11.5	>11.5
Magnesium (mg/dL)	LO	1.3-1.5	1.1-1.2	<1.1
Phosphorus (mg/dL)	LO	2.3-2.5	2.0-2.2	<2.0
CK (mg/dL)	N	1.25-1.5 x ULN	1.6-3.0 x ULN	$\geq 3.1 x$ ULN
Albumin (g/dL)	LO	2.8-3.1	2.5-2.7	<2.5
Total protein (g/dL)	LO	5.5-6.0	5.0-5.4	<5.0
Alkaline phosphatase (U/L)	N	1.1-2 x ULN	2.1-3 x ULN	$>3 x$ ULN
AST (U/L)	HI	1.1-2.5 x ULN	2.6-5 x ULN	$>5 x$ ULN
ALT (U/L)	HI	1.1-2.5 x ULN	2.6-5 x ULN	$>5 x$ ULN
Bilirubin, serum total (mg/dL) – when accompanied by any increase in Liver Function Test		1.1-1.25 x ULN	1.26-1.5 x ULN	$>1.5 x$ ULN
Bilirubin, serum total (mg/dL) – when Liver Function Test is normal		1.1-1.5 x ULN	1.6-2.0 x ULN	$>2.0 x$ ULN
Amylase (U/L)	N	1.1-1.5 x ULN	1.6-2.0 x ULN	$>2.0 x$ ULN
Lipase (U/L)	N	1.1-1.5 x ULN	1.6-2.0 x ULN	$>2.0 x$ ULN
Hematology				
	LO/HI/N ^c	Mild (Grade 1)	Moderate (Grade 2)	Severe (Grade 3)
Hemoglobin (women) change from baseline (g/dL)	LO	Any decrease- 1.5	1.6-2.0	>2.0
Hemoglobin (men) change from baseline (g/dL)	LO	Any decrease- 1.5	1.6-2.0	>2.0
White blood cell count (cell/mm ³)	HI	10,800-15,000	15,001-20,000	$>20,000$
	LO	2,500-3,500	1,500-2,499	$<1,500$
Lymphocytes (cell/mm ³)	LO	750-1,000	500-749	<500
Neutrophils (cell/mm ³)	LO	1,500-2,000	1,000-1,499	<1000
Eosinophils (cell/mm ³)	HI	650-1500	1501-5000	>5000
Platelets (cell/mm ³)	LO	125,000- 140,000	100,000- 124,999	$<100,000$
Coagulation				
PT (seconds)	HI	1.0-1.10 x ULN	1.11-1.20 x ULN	$>1.20 x$ ULN
International Normalized Ratio (INR) ^d	HI	1.1-1.5 x ULN	1.6-2.0 x ULN	$>2.0 x$ ULN
PTT or aPTT (seconds)	HI	1.0-1.2 x ULN	1.21-1.4 x	$>1.4 x$ ULN

^a Fasting.^b Non-fasting.^c Low, High, Not Graded.^d For INR, the values in the table are based on the Division of AIDS Table for Grading the Severity of Adult and Pediatric Adverse Events, 2009.

			ULN	
Fibrinogen (mg/dL)	HI	400-500	501-600	>600
	LO	150-200	125-149	<125
Urine				
Protein (dipstick)	HI	Trace	1+	2+
Glucose (dipstick)	HI	Trace	1+	2+
Blood (microscopic) - red blood cells per high power field (RBC/HPF)	HI	1-10	11-50	>50 and/or gross blood

RANGES TO CONVERT FDA SCALE (mg/dL) TO SI UNITS

Blood, Serum, or Plasma Chemistries^a	LO/HI/N^b	Mild (Grade 1)	Moderate (Grade 2)	Severe (Grade 3)
Glucose (mmol/L)	LO	3.61-3.38	3.05-3.60	≤ 3.04
	HI ^c	5.55-6.11	6.12-6.94	>6.94

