5. HEMOGLOBIN CUT-OFF VALUES

Where no institutional normal reference ranges is available for hemoglobin, the following cut-off values are proposed. It is imperative to note that there are no standard accepted normative values for hemoglobin in most African countries and therefore, the following recommendations are based on the review of several published sources and in consultation with the sites involved with the study. In the table below, 'simplified' means that the number of cut-off categories has been reduced to decrease complexity and facilitate understanding about eligibility. Similarly, 'adjusted for safety' means that the references may quote lower average or -2 SD values for hemoglobin but these values are considered to be too low for these subjects.

Group	Value (g/dL)		Reference	Outcome
Adult and HIV+	Male 12.1		Female 9.5 LLN value for local sites in Kenya and Uganda, current values being used in Phase 1	Values kept for consistency
Adolescent 16-18 yrs	Male 12.1		Female 9.5 Robins reference 10.4 g/dL for girls and 12.4 g/dL for boys	Values simplified to correspond to adult cut-offs
Adolescent 11-15 yrs	Male 11.0		Female 9.5 Robins reference 11.0 g/dL for girls and boys	Value adjusted down for boys, no change for girls
Children 6-10 yrs	11.0		Robins reference 10.7 g/dL for girls and boys	Value simplified
Children 2-5 yrs	11.0		Robins reference 10.4 g/dL for girls and boys, LLN value for local lab in Kenya 11.5 g/dL for girls and 14.5 g/dL for boys, Schellenberg reference 8.2-9.3 g/dL average anemic defined as <11.0 g/dL	Value simplified and adjusted for safety to 11.0 g/dL
Children 1-2 yrs	11.0		Schellenberg reference 8.0 g/dL average anemic defined as <11.0 g/dL, DMID toxicity table 11.0 g/dL	Value simplified and adjusted for safety to 11.0 g/dL

DMID US FDA Guidance Document Division of Microbiology and Infectious Diseases (DMID) Pediatric Toxicity Tables November 2007.

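### The SAP does not say whether the within-normal-limits rule overrides the change-only grading of adult hemoglobin; read literally, an in-range fall above 2.0 g/dL is reported as Grade 0 instead of Grade 3

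*SAP*

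**What the plan says.** SAP 7.2.1 opens with "In determining toxicity grades, the following rules will be applied". One of those rules is the override: "If a laboratory value falls within the grading as specified in the grading table but also within the local laboratory normal limits", the value counts as normal or Grade 0. The section names no exception.

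SAP Attachment 3 (laboratory toxicity grading for adults) repeats the override: "If a laboratory value falls within the grading as specified below but also within the local laboratory normal limits, the value is considered as normal". The next sentence reads "For hemoglobin only the change from reference is used for the grading". The hematology rows then grade men and women identically on the fall from baseline: any decrease up to 1.5 g/dL is Grade 1, 1.6 to 2.0 is Grade 2, and more than 2.0 is Grade 3. There is no absolute-value row. Protocol Attachment 2 carries the same two sentences and the same cut-offs.

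SAP 7.2.3 summarises laboratory data as the worst abnormality per period and regimen, with emphasis on Grade 3, plus a listing of subjects with abnormal findings. It plans no summary of hemoglobin values or mean changes.

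SAP Attachment 5, which SAP 7.2 cites for the laboratory analysis, gives adult hemoglobin cut-offs of 12.1 g/dL (men) and 9.5 g/dL (women), sourced as "LLN value for local sites in Kenya and Uganda, current values being used in Phase 1".

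**The concern.** A change-from-baseline scale is meant to pick up a large fall even when the subject ends inside the normal range. The override tests the absolute value. Applied to hemoglobin, it makes the grade depend first on whether the lower limit was crossed and only then on the size of the fall. A large fall from a comfortable baseline disappears, while a very small fall across the limit is graded.

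Safety is the primary objective, and hemoglobin is a parameter the protocol itself mentions. After MVA-BN-Filo, "events of decreased hemoglobin levels were reported" (Protocol 1.1.2.2), though less often than the other laboratory changes and without symptoms. The rabbit study in Protocol 1.1.1 also saw decreases, which were recovering and were judged not adverse. These are modest signals, but they are reason enough for the graded table to show large falls.

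The other laboratory outputs would not recover an in-range fall. A reset value is normal, so it does not enter the abnormal-findings listing. The normal-range fallback in SAP 7.2 applies only to tests without grades, and it too would call the value normal.

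**Working it through.** The plan states no figure on this point, so there is none to reproduce. The check applies the two rules together.

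**Inputs**
- Grade by fall: above 0 to 1.5 = Grade 1; 1.6-2.0 = Grade 2; above 2.0 = Grade 3 (SAP Attachment 3).
- Override: a value within local limits becomes Grade 0 (SAP 7.2.1).
- Lower limits (LLN): 12.1 g/dL men, 9.5 g/dL women (SAP Attachment 5).
- Assumptions: results to 0.1 g/dL; a value equal to the limit counts as within it.

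**Step 1. Smallest baseline from which a Grade 3 fall can be reset.** The smallest Grade 3 fall is 2.1, so the baseline must be at least LLN + 2.1.
- Men: 12.1 + 2.1 = 14.2 g/dL.
- Women: 9.5 + 2.1 = 11.6 g/dL.

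For Grade 2 (smallest fall 1.6): men 12.1 + 1.6 = 13.7; women 9.5 + 1.6 = 11.1 g/dL.

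**Step 2. Largest fall that can be reset** = baseline - LLN.
- Man at 16.0: 16.0 - 12.1 = 3.9 g/dL.
- Woman at 14.0: 14.0 - 9.5 = 4.5 g/dL.

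**Step 3. Worked cases**

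| Subject | Baseline to post-dose | Fall | Table grade | After override |
|---|---|---|---|---|
| Woman | 12.5 to 9.5 | 3.0 | 3 | 0 |
| Woman | 9.6 to 9.4 | 0.2 | 1 | 1 |
| Woman | 11.5 to 9.4 | 2.1 | 3 | 3 |
| Man | 15.0 to 12.5 | 2.5 | 3 | 0 |
| Man | 15.0 to 12.0 | 3.0 | 3 | 3 |

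The third and fifth rows show that a fall below the limit keeps its grade.

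**Step 4. Share of Grade 3 falls lost (illustration only).** The documents give no hemoglobin distribution. A simulation assumed baseline means of 14-16 g/dL (men) and 12-13.5 g/dL (women), baseline SD 1.0-1.4, and change with mean 0 and SD 0.7-1.0. About 0.2% (SD 0.7) to 2.3% (SD 1.0) of subjects then had a fall above 2.0 g/dL at a single sample. Of those falls, about 34-96% in men and 56-95% in women were reset. The width of these ranges shows how far the result depends on the assumptions.

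**Step 5. The opposite reading.** If hemoglobin were fully exempt, any decrease would be Grade 1. With symmetric random variation and no true change, about 50% of subjects would be at least Grade 1 at a single post-dose sample. So a full exemption also gives a poor table.

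**The case against.** The best defence is that the hemoglobin sentence in Attachment 3 is already a carve-out. It follows the override directly, and if only the change is used, the absolute value cannot undo it. It can also be argued that a hemoglobin value never falls within a scale made of changes. This reading is plausible, but it is not written: the sentence does not mention normal limits, and SAP 7.2.1 has no exception. Two programmers could reasonably produce different tables.

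Several limits on the point do stand:
- **Adverse event route.** Protocol 9.3.1 requires investigators to review laboratory results and record clinically relevant changes as adverse events, independently of the SAP-derived grade. A reader might infer that large falls vanish from the safety analysis altogether; this duty shows otherwise. It is discretionary, however, and SAP 7.2 describes such entries as abnormal values with a rise in grade.
- **Baseline.** A reader might infer that every adult starts inside the range. Protocol 4.1.1 bars low hemoglobin at screening only. Hematology is repeated on Day 1 before vaccination, and baseline is the last value before the prime.
- **Limits.** The 12.1 and 9.5 g/dL figures are proposed for use where no institutional range exists, and are sourced to Kenya and Uganda sites. Ranges at other laboratories are not given.
- **Number of subjects.** Cohorts 1 and 2a plan 660 + 132 = 792 adults. That is the population under the rule, placebo included, and not a count of those affected.

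**Conclusion.** The plan is wrong as written: a general override and a change-only scale conflict, and nothing says which governs. Under the literal reading, an adult fall above 2.0 g/dL that stays in range is Grade 0 in the only planned laboratory summary. At the documented limits this is possible from a baseline of 14.2 g/dL (men) or 11.6 g/dL (women). These thresholds move one for one with the local limit. The frequency is unknown.

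Two stronger conclusions are tempting. The first is that the laboratory table cannot show any lowering of hemoglobin. That goes too far, because falls that cross the limit are still graded and can be compared with placebo. The second is that the comparison between arms is biased. The documents do not support this, because the same rule applies to vaccine and placebo. What is lost is sensitivity to large in-range falls.

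**What to change.** State in SAP 7.2.1 and Attachment 3 which rule governs adult hemoglobin. Either of two forms would do:
1. The override does not reset adult hemoglobin falls of Grade 2 or 3 (1.6 g/dL or more from baseline).
2. The override stays, and falls of 1.6-2.0 and above 2.0 g/dL are tabulated by regimen and period regardless of the normal range.

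In both, keep the override for Grade 1, so that ordinary variation within the range is not counted. The second form leaves the grades untouched. It therefore avoids the jump that the first creates, where an in-range fall of 1.5 g/dL is Grade 0 and one of 1.6 is Grade 2.

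The cost is a sentence in each place or one extra table, with data already collected. The first form will show somewhat more Grade 2-3 hemoglobin decreases in both vaccine and placebo columns. With either form, in-range falls of up to 1.5 g/dL remain Grade 0, and a very small fall across the limit remains Grade 1.

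Protocol Attachment 2 has the same two sentences, and the laboratory pausing rule in Protocol 9.3.2 refers to Grade 3 abnormalities. These passages must be reconciled with each other and with the SAP. This point takes no position on what the pausing rule should be.

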7.2.2. Data Handling Rules

In case a laboratory test result is *censored* (no numeric value is available, but only a verbatim term) then a numeric value will be imputed:

- For integer x :
 - If the value is $< x$ then impute with $x-1$.
 - If the value is $> x$ then impute with $x+1$.

- For mantissa (decimal part) x :
 - If the value is $< y.x$ then impute with $y.x-0.1$ (if x has 1 decimal place of precision).
 - If the value is $> y.x$ then impute with $y.x+0.1$ (if x has 1 decimal place of precision).

Remark: The value added or subtracted from the mantissa should follow from its mantissa.

Example:

If value is < 5 or > 10 impute with 4 and 11 respectively.
 If value is < 5.3 or > 10.7 then impute with 5.2 and 10.8 respectively.
 If value is < 5.32 or > 10.73 then impute with 5.31 and 10.74 respectively.

7.2.3. Analysis Methods

Laboratory abnormalities (except CD4+ cell counts in HIV-infected subjects) will be determined in accordance with the toxicity grading tables (Attachment 3 and Attachment 4), and in accordance with the normal ranges of the clinical laboratory. The worst abnormalities following vaccination will be summarized (ie, showing number and percentage) by regimen and presented per period/phase, with special attention to Grade 3 toxicities. Focus will be on clinical abnormalities that occur during Post-dose 1, Post-dose 2 and Post-dose 3 periods, as well as the Regimen Phase. Similar tables for worst abnormalities will be provided pooled by vaccine (dose). A listing will also be provided for subjects with any abnormal laboratory findings following vaccination. For CD4+ cell counts in HIV-infected subjects, a listing will also be generated.

7.3. Vital Signs and Physical Examination Findings

Vital sign abnormalities will be determined in accordance with the DMID Vital Signs Toxicity Grading (Attachment 3). For Cohort 3, the vital signs will be summarized and listed. The summary will be presented per time point and showing the mean, standard deviation, median, Q1, Q3, minimum and maximum. For the other cohorts (ie, Cohorts 1, 2a and 2b), only a listing of subjects with vital sign abnormalities will be provided because the assessments are only done at screening and pre-vaccination (ie, prior to Doses 1 and 2).

It is important to note that a full physical examination is only conducted at screening. At other visits, only abbreviated, symptom-directed examinations are performed per the investigator's discretion. Therefore, only a listing of subjects with physical examination findings (ie, abnormalities) following vaccination will be provided. Also, any clinically relevant vital signs or physical examination abnormalities occurring from signing of the ICF onwards until 42-day post-second vaccination and again from third vaccination (only for subjects in Cohort 1 substudy) until 28 days thereafter is recorded on the AE page of the eCRF and will be analyzed as AE.

7.4. Electrocardiogram

Note that a single, 12-lead electrocardiogram was performed at screening for subjects ≥ 18 years (Cohorts 1 and 2a) and interpreted locally. Additional electrocardiogram monitoring could be done at other time points during the study only if clinically indicated based on signs and

symptoms. Therefore, only a listing of subjects with an electrocardiogram abnormality following vaccination will be generated.

REFERENCES

1. Clinical Protocol VAC52150EBL2002 Amendment 3: A Randomized, Observer-blind, Placebo-controlled, Phase 2 Study to Evaluate the Safety, Tolerability and Immunogenicity of Different Prime-boost Regimens of the Candidate Prophylactic Vaccines for Ebola Ad26.ZEBOV and MVA-BN-Filo in Healthy Adults, Including Elderly Subjects, HIV-infected Subjects, and Healthy Children in Two Age Strata in Africa. Walter Reed Army Institute of Research and Janssen Vaccines & Prevention B.V. (May 2017).
3. VAC52150EBL2002-Independent Data Monitoring Committee Charter. Janssen Vaccines & Prevention B.V. (September 2016).
4. VAC52150EBL2002-Independent Data Monitoring Committee Statistical Analysis Plan Amendment 1. Crucell Holland B.V. (September 2015).
5. Centers for Disease Control and Prevention. Clinical Growth Chart. Available at: http://www.cdc.gov/growthcharts/clinical_charts.htm. Accessed 10 March 2015.
6. Centers for Disease Control and Prevention Clinical Growth Chart Percentile Data File. Available at: https://www.cdc.gov/growthcharts/percentile_data_files.htm. Accessed 28 May 2018.

ATTACHMENTS

